### 4.3 JUSTIFICATION FOR DOSE

The choice of the dose of 20 mg BID SAR443820 is based on all available nonclinical and clinical data at the time of protocol development.

The NOAEL was █ mg/kg/day in nonhuman primates (cynomolgus monkeys). A █ this NOAEL was implemented as the human exposure cap in Phase 1 single ascending dose (SAD) and multiple ascending dose (MAD) studies.

Overall, in the first-in-human study, SAR443820 up to a highest single dose of █ mg and multiple 14-day dose of 20 mg BID, was found to be safe and well tolerated. In the Phase 1a SAD study, there were no SAEs. All the TEAEs were of mild to moderate intensity except 1 severe TEAE (blood creatine phosphokinase [CPK] increase of Grade 3) reported in the placebo group. Since convulsions

[REDACTED]. In the MAD study, no SAEs, other than dose limiting AEs or laboratory findings, were reported. All the AEs reported in the MAD study were of mild to moderate intensity. At 20 mg BID, the highest dose administered, the mean observed  $C_{max}$  was 1.22  $\mu\text{M}$  and the  $AUC_{0-24\text{h}}$  (corresponding to  $AUC_{0-12\text{h}} * 2$ ) was 15.0  $\mu\text{M} * \text{hour}$ . These values are estimated to be [REDACTED], respectively.

The dose of 20 mg BID SAR443820 is estimated to provide a high level of target engagement required for obtaining a clinical effect. Internal preclinical data in animal models suggest CNS [REDACTED] is a predictor of a clinical therapeutic effect. Preliminary data indicate a good penetration of SAR443820 in CSF with mean values of the CSF/unbound plasma ratio of at least 0.81 and 1.27 before and after plasma  $t_{max}$ , respectively. A preliminary PBPK model indicates that at a dose of 20 mg BID, [REDACTED] [REDACTED], which has been determined in vivo using the pS166-RIPK1 inhibitor assay in PBMC.

Therefore, 20 mg BID, which has been demonstrated to be well tolerated in healthy subjects, is selected for this Phase 2 study to achieve the best potential treatment effectiveness in participants with ALS while maintaining [REDACTED] to the NOAEL exposure in the nonhuman primate study.

#### **4.4 END OF STUDY DEFINITION**

The end of the study is defined as the date of the last visit of the last participant in the study or last scheduled assessment and/or procedure shown in the SoA for the last participant in the study globally.

A participant is considered to have completed the study if he/she has completed all phases of the study, including the last visit or the last scheduled procedure as shown in the SoA ([Section 1.3](#)).

## 5 STUDY POPULATION

Prospective approval of protocol deviations to recruitment and enrollment criteria, also known as protocol waivers or exemptions, is not permitted.

### 5.1 INCLUSION CRITERIA

Participants are eligible to be included in the study only if all of the following criteria apply:

#### Age

I 01. Participants must be 18 to 80 years of age inclusive, at the time of signing the informed consent form.

#### Type of participant and disease characteristics

I 02. Participants must have been diagnosed with possible, clinically probable ALS, clinically probable laboratory-supported ALS, or clinically definite ALS according to the revised version of the El Escorial World Federation of Neurology criteria (22).

I 03. Participants must have an ALS disease duration (from first symptom onset to the screening visit)  $\leq 2$  years.

I 04. Participants must have an ALSFRS-R prestudy slope  $\geq 0.5$  points/month prior to the screening visit ( $\Delta$ ALSFRS-R = (48 - ALSFRS-R score at the screening visit)/duration in months between the screening visit and disease onset).

I 05. Participants must have an upright (sitting position) SVC  $\geq 60\%$  of the predicted value as adjusted for sex, age, and height at the screening visit.

I 06. Participants must be able to swallow the study tablets at the screening visit.

I 07. Participants must either not currently receiving riluzole or on a stable dose of riluzole for at least 4 weeks before the screening visit. Participants receiving riluzole are expected to remain on the same dose throughout the duration of the study.

I 08. Participants must either not currently receiving edaravone or are on the approved standard schedule of edaravone treatment. Participants receiving edaravone must have completed at least 1 cycle of treatment before the screening visit and are expected to continue edaravone treatment throughout the duration of the study.

#### Weight

I 09. Participants with a body weight no less than 45 kg and body mass index (BMI) no less than  $18.0 \text{ kg/m}^2$  at the screening visit.

## **Sex, contraceptive/barrier method and pregnancy testing requirements**

### **I 10. All**

Contraceptive use by men and women should be consistent with local regulations regarding the methods of contraception for those participating in clinical studies.

#### **a) Male participants**

Male participants are eligible to participate if they agree to the following during the study period and for at least 92 days following their last dose of the IMP:

- Refrain from donating or cryopreserving sperm  
PLUS, either:
  - Be abstinent from heterosexual intercourse as their preferred and usual lifestyle (abstinent on a long-term and persistent basis) and agree to remain abstinent  
OR
  - Must agree to use contraception/barrier method as detailed below:
    - A male condom and an additional highly effective contraceptive method as described in Appendix 4 ([Section 10.4](#)) when having sexual intercourse with a woman of childbearing potential (WOCBP) who is not currently pregnant.

#### **b) Female participants**

Female participants are eligible to participate if they are not pregnant or breastfeeding and 1 of the following conditions applies:

- Are woman of nonchildbearing potential (WONCBP) as defined in Appendix 4 ([Section 10.4](#))  
OR
- Are WOCBP and agree to use a contraceptive method that is highly effective (with a failure rate of <1% per year), preferably with low user dependency, as described in Appendix 4 ([Section 10.4](#)) during the study intervention period (to be effective before starting the study intervention) and for at least 32 days after the last administration of the IMP and agree not to donate or cryopreserve eggs (ova, oocytes) for the purpose of reproduction during this period.
- WOCBP must have a negative highly sensitive pregnancy test within 24 hours before the first administration of the study intervention, see [Section 8.2.6](#).
- If a urine test cannot be confirmed as negative (eg, an ambiguous result), a serum pregnancy test is required. In such cases, the participant must be excluded from participation if the serum pregnancy result is positive.

## **Informed consent**

### **I 11. Participants must be capable of giving signed informed consent as described in Appendix 1 ([Section 10.1](#)), which includes compliance with the requirements and restrictions listed in the informed consent form (ICF) and in this protocol.**

### **Criteria added in amended protocol**

I 12. Participants must either not currently be receiving the combination of sodium phenylbutyrate and taurursodiol or are on the approved standard schedule of the combination of sodium phenylbutyrate and taurursodiol treatment for at least 4 weeks before the screening visit. Participants receiving the combination of sodium phenylbutyrate and taurursodiol are expected to remain on the approved standard schedule throughout the duration of the study

## **5.2 EXCLUSION CRITERIA**

Participants are excluded from the study if any of the following criteria apply:

### **Medical conditions**

E 01. Participants with a history of seizure or epilepsy (History of febrile seizure during childhood is allowed).

E 02. Participants with central IV lines, such as a peripherally inserted central catheter (PICC) or midline or port-a-cath lines.

E 03. Participants with a significant cognitive impairment, psychiatric disease, other neurodegenerative disorder (eg, Parkinson disease or AD), substance abuse, other causes of neuromuscular weakness, or any other condition that would make the participants unsuitable for participating in the study or could interfere with assessment or completing the study in the opinion of the Investigator.

E 04. Participants with a history of recent serious infection (eg, pneumonia, septicemia) within 4 weeks of the screening visit; infection requiring hospitalization or treatment with IV antibiotics, antivirals, or antifungals within 4 weeks of screening; or chronic bacterial infection (such as tuberculosis) deemed unacceptable as per the Investigator's judgment.

E 05. Participants with an active herpes zoster infection within 2 months prior to the screening visit.

E 06. Participants with a documented history of attempted suicide within 6 months prior to the screening visit, present with suicidal ideation of category 4 or 5 on the Columbia Suicide Severity Rating Scale (C-SSRS), or in the Investigator's judgment are at risk for a suicide attempt.

E 07. Participants with a history of unstable or severe cardiac, pulmonary, oncological, hepatic, or renal disease or another medically significant illness other than ALS precluding their safe participation in this study.

E 08. Participants who are pregnant or are currently breastfeeding.

E 09. Participants with a known history of allergy to any ingredients of SAR443820 (mannitol, lactose monohydrate, sodium starch glycolate, colloidal silicon dioxide, magnesium stearate, hypromellose, titanium dioxide, polyethylene glycol, and microcrystalline cellulose).

### **Prior/concomitant therapy**

E 10. Participants who have received any strong or moderate CYP3A4 inhibitors or strong CYP3A4 inducers listed in Appendix 10, [Section 10.10, Table 8](#) within the specified washout period before the screening visit.

E 11. Participants who have received a live vaccine within 14 days before the screening visit.

### **Prior/concurrent clinical study experience**

E 12. Participants with concurrent participation in any other interventional clinical study or who have received treatment with another investigational drug (eg, sodium phenylbutyrate or taurursodiol) within 4 weeks or 5 half-lives of the investigational agent before the screening visit, whichever is longer.

E 13. Participants who have received stem cell or gene therapy for ALS at any time in the past.

### **Diagnostic assessments**

E 14. Participants with a positive human immunodeficiency virus (HIV) antibody test.

E 15. Participants with abnormal laboratory test(s) at the screening visit including the following:

- Alanine aminotransferase (ALT) or aspartate aminotransferase (AST)  $>3.0 \times$  upper limit of normal (ULN)
- Bilirubin  $>1.5 \times$  ULN unless the participant has documented Gilbert syndrome (isolated bilirubin  $>1.5 \times$  ULN is acceptable if bilirubin is fractionated and direct bilirubin is  $<35\%$ )
- Serum albumin  $<3.5$  g/dL
- Estimated glomerular filtration rate  $<60$  mL/min/1.73 m^2 (Modification of Diet in Renal Disease [MDRD])
- Other abnormal laboratory values or ECG changes that are deemed clinically significant as per the Investigator's judgment

E 16. Participants with hepatitis B surface antigen (HBsAg) or antihepatitis B core antibodies (anti-HBcAb) at the screening visit or within 3 months prior to the first dose of the study intervention. Serologies consistent with a resolved infection or vaccination, such as the presence of HBsAb, may not exclude potential participants from the trial.

E 17. Participants with a positive hepatitis C antibody test result at the screening visit or within 3 months prior to starting the study intervention. NOTE: Participants with a positive hepatitis C antibody test due to prior resolved disease can be enrolled only if a confirmatory negative hepatitis C RNA test is obtained.

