- i* A full physical examination will be performed at the screening visit, and a brief physical examination will be performed at all other visits. The skin and lymph nodes need to be checked at each site visit.
- j* Vital signs include blood pressure, heart rate, respiratory rate, and temperature.
- k* Postdose vital signs should be measured at least 10 minutes after the second PK sample collection (recommended to be measured within 10 to 30 minutes after the second PK sample collection).
- l* The "Since Last Visit" version of the C-SSRS will be used.
- m* A full neurological examination will be performed at the screening visit, and a brief neurological examination pertaining to cranial nerves, coordination/cerebellar function, reflexes, and motor function will be performed at other visits.
- n* Substances include drugs of abuse, alcohol, tobacco, and caffeine.
- o* Only in female participants, if needed to establish menopausal status.
- p* Only liver chemistry monitoring will be conducted, which includes testing of alanine transaminase (ALT), aspartate aminotransferase (AST), bilirubin direct, bilirubin total and alkaline phosphatase.
- q* Optional one-time blood draw for DNA analysis can be completed at either Week 2 or Week 4 visit.
- r* The muscles measured include both upper-limb and lower-limb muscle groups. Bilateral hand grip will be measured using a Jamar grip dynamometer and all other muscles included in this study will be measured using a handheld dynamometer.
- t* The IMP can be taken under either fasting or non-fasting condition.
- u* Two samples for PK will be collected at this visit, 1 within 15 minutes to 1 hour and another within 1 to 3 hours after the morning dose of IMP. There will be at least 45 minutes between the 2 samplings.
- v* One sample for PK will be collected within 1 hour before the morning dose of IMP.
- w* One sample for PK will be collected within 15 minutes to 3 hours after the morning dose of IMP.
- x* The cytokines measured in this study include IFN- $\gamma$ , IL-1 $\beta$ , IL-2, IL-4, IL-6, IL-8, IL-10, IL12p70, IL-13, and TNF- $\alpha$ . The chemokines measured in this study include eotaxin-1, eotaxin-3, TARC, IP-10, MIP1 $\alpha$ , MIP1 $\beta$ , MCP1, and MCP4.
- y* This assessment will not be conducted in China (see Appendix 8 [[Section 10.8](#)]).

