## 2.3 BENEFIT/RISK ASSESSMENT

### 2.3.1 Risk assessment

**Table 1 - Risk assessment (identified risk of clinical significance)**

Identified risk of clinical significance	Summary of data/rationale for risk	Mitigation strategy
Study intervention(s)		
ALT increase/Drug induced liver injury (DILI)	During clinical trials with SAR443820, mild-severe ALT increases have been reported, including 2 SUSARs with total bilirubin increase $> 2$ ULN reported in the ALS patients. These events often involved patients who were also taking concomitant medications that are known to induce liver function abnormalities, or who had concomitant diseases that could also affect ALT level.	Implemented through an USM dated on 5th December 2023, all participants in Part A are requested to conduct weekly liver chemistry monitoring and all participants in Part B are requested to pause SAR443820 immediately until DMC recommendation to resume dosing based on benefit-risk considerations when Part A data is available. Additionally, all participants are requested to limit their alcohol consumption during the whole study period.  Detailed instructions to be followed in case of the occurrence of an AESI of ALT increase $> 3$ ULN are described in Appendix 6 in this protocol, and cover ALT monitoring, IMP administration, etiology assessment and IMP rechallenge.

Abbreviations: ALT=alanine transaminase; DILI=drug induced liver injury; IMP=investigational medicinal product, SUSAR=suspected unexpected serious adverse event, ULN=upper limit normal, USM=urgent safety measure, AESI=adverse event of special interest

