**Table 7 - Protocol-required laboratory tests**

Laboratory tests	Parameters
Hematology	
Platelet count
 
Red blood cell (RBC) count
 
Hemoglobin
 
Hematocrit
 
RBC indices:
 
Mean corpuscle volume (MCV)
 
Mean corpuscle hemoglobin (MCH)
 
%Reticulocytes
 
White blood cell (WBC) count with differential:
 
Neutrophils
 
Lymphocytes
 
Monocytes
 
Eosinophils
 
Basophils

Clinical chemistry a	
Blood urea nitrogen (BUN)
 
Creatinine
 
Glucoseb
 
Potassium
 
Sodium
 
Calcium
 
Aspartate aminotransferase (AST)/ Serum glutamic-oxaloacetic transaminase (SGOT)
 
Alanine aminotransferase (ALT)/ Serum glutamic-pyruvic transaminase (SGPT)
 
Alkaline phosphatasec
 
Albumin
 
Creatine phosphokinase (at screening visit only)
 
Total and direct bilirubin
 
Total protein

Routine urinalysis	
 
• Specific gravity
 
• pH, glucose, protein, blood, ketones, bilirubin, urobilinogen, nitrite, leukocyte esterase by dipstick
 
• Microscopic examination (if blood or protein is abnormal)
 
• Serum or highly sensitive urine human chorionic gonadotropin (hCG) pregnancy test (as needed for women of childbearing potential)d
 

Pregnancy testing	

Laboratory tests	Parameters
Other screening tests	

• Follicle-stimulating hormone (FSH) and estradiol (as needed in women of non-childbearing potential only)

• Serology (human immunodeficiency virus [HIV] antibody, hepatitis B surface antigen [HBsAg], and hepatitis C virus antibody or specify other tests)

• All study-required laboratory tests will be performed by a central laboratory.

NOTES :

- a Details of liver chemistry stopping criteria and required actions and follow-up are given in Appendix 6 ([Section 10.6](#)) [Liver and other safety. Suggested actions and follow-up assessments [and study intervention rechallenge guidelines]. All events of ALT >3 × ULN, which may indicate liver injury, must be reported to Sponsor in an expedited manner (refer to the section on AESIs [[Section 8.3.8](#)]). Clinical laboratory findings of ALT >3 ULN and bilirubin >2 × ULN (>35% direct bilirubin), which may suggest severe liver injury (possible Hy's Law), must be reported to Sponsor in an expedited manner.

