**E) Is a congenital anomaly/birth defect**

**F) Is a suspected transmission of any infectious agent via an authorized medicinal product**

**G) Other situations:**

- Medical or scientific judgment should be exercised by the Investigator in deciding whether SAE reporting is appropriate in other situations such as significant medical events that may jeopardize the participant or may require medical or surgical intervention to prevent 1 of the other outcomes listed in the above definition. These events should usually be considered serious.
  - Note: The following list of medically important events is intended to serve as a guideline for determining which condition has to be considered as a medically important event. The list is not intended to be exhaustive:
- Intensive treatment in an emergency room or at home for:
  - Allergic bronchospasm
  - Blood dyscrasias (ie, agranulocytosis, aplastic anemia, bone marrow aplasia, myelodysplasia, pancytopenia, etc)
  - Convulsions

- Development of drug dependence or drug abuse
- ALT  $>3 \times$  ULN + total bilirubin  $>2 \times$  ULN or asymptomatic ALT increase  $>10 \times$  ULN
- Suicide attempt or any event suggestive of suicidality
- Syncope, loss of consciousness (except if documented as a consequence of blood sampling)
- Bullous cutaneous eruptions

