Potentially clinically significant abnormality (PCSA) analyses will be performed based on the PCSA list currently in effect at Sanofi at the time of the database lock. For parameters for which no PCSA criteria are defined, similar analyses will be done using the normal range, if applicable.

Analyses according to PCSA (normal range) will be performed based on the worst value during the treatment-emergent period, using all measurements (either local or central, either scheduled, nonscheduled or repeated).

For laboratory variables, vital signs and ECG variables above, the incidence of participants with at least one PCSA during the on-treatment period for Part A and Part A + Part B will be summarized regardless of the baseline level and according to the following baseline status categories:

- Normal/missing
- Abnormal according to PCSA (normal range) criterion or criteria

Additional analyses for drug-induced liver injury

The following additional analyses will be performed for drug-induced liver injury in Part A and Part A + Part B:

- Time to onset of the initial alanine aminotransferase (ALT) or aspartate aminotransferase (AST) elevation ($>3 \times$ ULN) and total bilirubin elevation ($>2 \times$ ULN) during the treatment-emergent period will be analyzed using Kaplan-Meier method.
- A graph of the distribution of peak values of ALT versus peak values of total bilirubin during the treatment-emergent period will be provided.
- For each liver function test (eg, ALT), participants having experienced a PCSA (eg, ALT >5 ULN) will be summarized using the following categories: Returned to baseline PCSA status (or returned to value \leq ULN in case of missing baseline) before last IMP dose, Returned to baseline PCSA status after last IMP dose, Never returned to baseline PCSA status, No assessment after elevation. This summary will be performed by categories of elevation (ALT >3 , >5 , >10 , >20 ULN).

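### The SAP's bilirubin onset analysis and ALT-versus-bilirubin plot ignore baseline bilirubin and the direct fraction, so a pre-existing unconjugated elevation can be counted as treatment-emergent

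*Protocol*

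**What the plan says.** **Entry.** Protocol 5.2, E 15, excludes screening bilirubin above 1.5 × "ULN unless the participant has documented Gilbert syndrome (isolated bilirubin" above that limit being tolerated on a condition: a value above 1.5 × "ULN is acceptable if bilirubin is fractionated and direct bilirubin is" below 35%. No maximum total bilirubin is attached to the exception.

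**Combined ALT and bilirubin event in the protocol.** There are two wordings.
- Appendix 2, Table 7 note a, asks for expedited reporting of "Clinical laboratory findings of ALT >3 ULN and bilirubin >2 × ULN (>35% direct bilirubin), which may suggest severe liver injury (possible Hy's Law").
- Appendix 3, 10.3.2, lists among medically important events an ALT above 3 × "ULN + total bilirubin" above 2 × ULN, with no condition on the direct fraction.

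The risk table in 2.3.1 also speaks of total bilirubin only: "including 2 SUSARs with total bilirubin increase" above 2 ULN.

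**SAP 3.6.3.1, additional analyses for drug-induced liver injury.** Time to the first ALT or AST elevation (above 3 × ULN) and total bilirubin elevation (above 2 × "ULN) during the treatment-emergent period will be analyzed using Kaplan-Meier method". In addition, "A graph of the distribution of peak values of ALT versus peak values of total bilirubin during the treatment-emergent period will be provided". Neither item mentions baseline bilirubin, the direct fraction or Gilbert status.

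**Data collected.** The liver-only visits measure "aspartate aminotransferase (AST), bilirubin direct, bilirubin total and alkaline phosphatase" as well as ALT (Protocol 1.3.1, footnote p). SAP 3.6.3.1 lists direct bilirubin as a separate liver variable.

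**The concern.** A time-to-onset analysis should count something that begins on treatment. E 15 can admit participants whose usual bilirubin is raised and mainly unconjugated, at any level. The SAP's onset rule has no step that removes values already above the threshold before the first dose. The plot has no way to tell such a person from one whose conjugated bilirubin rose on treatment.

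Drug-induced liver injury is the identified risk behind Amendment 05 and the Part B pause, and any resumption depends on review of Part A data. The protocol reports very few combined ALT and bilirubin cases, so one or two points with another explanation could affect how the by-arm display is read. The difference between Table 7 note a and 10.3.2 adds to this: the SAP outputs do not show which of the two wordings a case meets.

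**Working it through.** **Step 1. What the Kaplan-Meier sentence can mean.** It joins an ALT/AST criterion and a bilirubin criterion with a plain conjunction. It can describe two curves (time to ALT/AST above 3 × ULN; time to total bilirubin above 2 × ULN) or one curve for the joint event. The SAP does not say which.

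**Step 2. Three example patterns under each rule.** Values are multiples of ULN.

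| Pattern | ALT | Total bilirubin | Direct | Table 7 note a | 10.3.2 | SAP bilirubin curve, if separate | SAP joint event |
|---|---|---|---|---|---|---|---|
| Unconjugated, normal ALT | 0.8 | 2.5 | 15% | no | no | **yes** | no |
| Unconjugated, raised ALT | 4 | 2.5 | 15% | no | yes | yes | **yes** |
| Conjugated, raised ALT | 4 | 2.5 | 60% | yes | yes | yes | yes |

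- The first row is an event only on the separate-curve reading. If the 2.5 × ULN was already present at baseline and persists, the onset falls at the first on-treatment sample.
- The second row meets 10.3.2 and the joint SAP event but not note a.
- On the plot, each participant contributes two peaks that need not share a date. A person constitutionally above 2 × ULN therefore moves to high values on both axes with any passing ALT rise.

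**Step 3. Size.** The documents state no count or rate on this point, so there is no plan figure to reproduce. The only input from the documents is N = 261 planned participants. The rest are assumptions:
- g, share with Gilbert syndrome: 2% to 10%
- q, share of those above 2 × ULN on study: 10% to 50%
- p, share with ALT above 3 × ULN, independent of Gilbert status: 3% to 15%

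Bilirubin criterion alone, N × g × q:
- low: 261 × 0.02 × 0.10 = 0.52
- high: 261 × 0.10 × 0.50 = 13.05

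Bilirubin and ALT together, N × g × q × p:
- low: 261 × 0.02 × 0.10 × 0.03 = 0.016
- high: 261 × 0.10 × 0.50 × 0.15 = 1.96

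For the 174 planned on SAR443820 the corresponding ranges are 0.35 to 8.7 and 0.01 to 1.3.

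**Step 4. The right comparator.** The 2 SUSARs in Protocol 2.3.1 are ALT increases accompanied by raised bilirubin. They compare with the combined range (0.02 to 2), not with the bilirubin-only range (0.5 to 13).

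**Step 5. Effect of adding the direct-fraction condition.** Requiring more than 35% direct removes the first two rows of the table from the bilirubin curve and the combined count, and keeps the third.

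**The case against.** Three stronger readings are tempting, and the documents support none of them.

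- **That the SAP presents benign bilirubin as Hy's Law.** The SAP never uses the term, draws no such region on the plot and plans no count of such cases. Raised bilirubin with normal ALT is high on one axis only and fails both protocol rules for the combined event.
- **That E 15 is the fault.** E 15 already requires the elevation to be isolated, fractionated and under 35% direct, which is the same logic as Table 7 note a. It explains how such participants can be present; it needs no change.
- **That the SAP departs from the protocol's definition.** The direct-fraction condition stands only in note a. The SAP's 2 × ULN total-bilirubin threshold agrees with 10.3.2 and with the risk table in 2.3.1. The two protocol passages also serve different purposes: one triggers expedited reporting, the other is a non-exhaustive guide to seriousness.

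Existing safeguards count too. Direct bilirubin is analysed on its own. PCSA incidence is split by baseline status, and the third liver output tracks return to baseline PCSA status. AESIs and SAEs are listed individually. Appendix 6 requires conjugated bilirubin in confirmed cases of ALT above 5 × ULN and mentions a test for Gilbert's disease. Any confirmed ALT above 3 × ULN is reported within 24 hours as an AESI, so no such case depends on the bilirubin wording to reach the sponsor. The sponsor's PCSA list is not in the documents, so whether it contains a direct-fraction criterion cannot be checked.

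All of this stands, and it limits the point. It does not repair the onset curve or the plot: neither is tied to baseline status, to the PCSA list or to the direct fraction.

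**Conclusion.** The point holds in a narrow form, and its place is SAP 3.6.3.1. The onset analysis does not say whether its event is separate or joint, and it has no rule for values already above threshold at baseline. The plot cannot distinguish an unconjugated, pre-existing elevation from a new conjugated one. Separately, Table 7 note a and 10.3.2 word the combined event differently.

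The number affected cannot be derived from the documents. On the assumed rates above it is about 0.5 to 13 participants if bilirubin is its own Kaplan-Meier event, and about 0.02 to 2 for the combined pattern, so the latter may be nil. The bilirubin-only range applies only on the separate-curve reading.

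Severity is low. SAP 3.6 makes the safety analysis descriptive with no tests, and type I error, power and sample size are untouched. The change is still worth making because it is cheap and concerns the risk that led to the Part B pause.

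**What to change.** In SAP 3.6.3.1:

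1. State whether the Kaplan-Meier event is separate (one curve each for ALT/AST and bilirubin) or joint. Do not count a value already above threshold at baseline as an onset, or show those participants separately.
2. Beside the total-bilirubin version, give the bilirubin onset curve and the combined ALT/bilirubin count with the Table 7 note a condition (more than 35% direct). Show results without a direct fraction as unclassified.
3. On the peak plot, mark participants with raised baseline bilirubin and those whose direct fraction was 35% or less at the bilirubin peak.

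In the protocol, Table 7 note a and 10.3.2 must be reconciled, or their different purposes stated. Which wording should govern reporting is for the sponsor to decide.

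**Cost.** SAP wording and one extra display. No new data are needed, because direct bilirubin is part of the scheduled liver tests. The downside is small: some local-laboratory results may lack the direct fraction and would be unclassified. The total-bilirubin version stays alongside, so no case disappears from view.
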